To further explore the concept of Gadoterate-based differential outcomes, two separate interpretations for each Gadoterate-enhanced MRI will be recorded in the research database: an interpretation based upon only the non-contrast images and the full interpretation of the whole exam (non-contrast + contrast images). We will subsequently record the *predicted* outcome data, as described above (diagnoses, subsequent imaging studies, pathology results, therapies, and projected related costs), that would be associated with the more limited interpretation of the non-contrast images. Comparison to the actual outcomes of that patient will subsequently be analyzed. This is both feasible and straightforward since the vast majority of the clinical MRI indications in this study have a well-defined diagnostic/therapeutic pathway – i.e. a solitary liver lesion demonstrated to be malignant by contrast MRI would result in chemo-embolization, whereas an indeterminate result based on non-contrast would lead to a liver biopsy [18]. Another example: Cystic renal lesions which cannot be completely characterized without contrast are typically followed with serial imaging exams to check for growth, whereas demonstration of a simple cyst by contrast-enhanced exam will typically result in no further imaging.

Statistics:

Previously-tested GBCAs in chronic kidney failure patients have resulted in 10-25% rates of decreased GFR, depending upon the study, with most investigations recording rates in the range of ~15% [5]. Based upon various data thus far (noted above), the rate is expected to be no more than 5% using Gadoterate;

therefore if we wish to detect a significantly lower rate of renal complications with a power of 90% and a 5% significance, then a sample size of approximately 136 patients receiving Gadoterate is properly powered to address Aim 1. The non-Gadoterate control arm does not need to be as large for analysis of Aim 1, however, it will consist of 136 patients as well, to properly power analysis of Aim 2. This number is expected to be more than sufficient considering that significant interpretive and outcome differentials are anticipated at a far greater rate than 5%, between the non-contrast image and contrast image evaluations.

Study Procedures

Subject selection

Inclusion Criteria: GFR less than 30 ml/min, but not on dialysis, with indications for MRI as described above. GFR will be calculated in the same fashion as in current use in our department:

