Gadoterate will be the only contrast agent used. There is no placebo and no blinding is needed. Gadoterate will be provided by Guerbet pharmaceuticals and will be stored in the identical fashion that all Gadolinium agents are stored in the department (see attached package insert). Gadoterate will be administered according to its standard weight-based protocol, 0.2 mL/kg [8].

Administrative Organization

This will be a single site study conducted at Loyola University Medical Center. Patient recruitment and participation from the referring clinicians in the hepatology, neurosurgery, neurology, neurosurgery, and urology divisions will be coordinated by an MRI nurse coordinator, who will devote 10% time to this project. In addition, all blood draws and patient follow up will be coordinated by the nurse coordinator. All imaging will be conducted on-site. The standard LUMC laboratory locations and procedures will be used to calculate GFR from the patients' serum.

The clinical research office (CRO) will assist with statistical data analysis.

Safety and Monitoring

As with any intravenous contrast agent, numerous nonspecific adverse (mostly allergic-type) reactions are possible, though rare (see attached package insert), for Gadoterate, and no more common than in any other agent in clinical use. The most serious adverse event is difficulty breathing. Patient safety related to

such events will be monitored by direct technician and nurse supervision at the time of the exam and in the immediate period following – this is standard department protocol for all contrast MRI exams.

The main additional serious adverse reaction is the one being specifically monitored in this study - renal toxicity. Monitoring of this will be done by 48-72 hour post-exam serum creatinine evaluation, as described above. In addition, long-term toxicity in the form of NSF will be evaluated by detailed phone follow-up, designed to identify any potential signs of NSF (see Figure 2). In the event of a positive response to 3 or more of the questions in the questionnaire, the patient will be assisted in scheduling a Dermatology appointment at LUMC.

The PI ([name]) and the nurse coordinator will be responsible for tracking and assessing any adverse events.

Reporting of Adverse Events or Unanticipated Problems involving Risk to Participants or Others:

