Any adverse events, as described above or unanticipated, involving risk to participants, will be promptly submitted to the IRB in accordance with established guidelines.

In addition, all data related to renal function and NSF will be routinely reviewed by the PI every 3 months.

Analysis

Image analysis: As described above, each MRI exam will be independently interpreted by 2 participating sub-specialty-trained (either neuro or body) radiologists, with the readers blinded to history and prior exams. For both contrast and non-contrast exams, the images will be viewed in the standard clinical fashion (Intellispace PACS system). For the contrast exams, the interpreting radiologists will first render an evaluation based upon *only* the non-contrast images - these interpretations will be recorded only within the research database. As described earlier, this will enable evaluation of the added advantages of the contrast agent. The overall contrast-exam interpretations, as well as the interpretations of the non-contrast exams, will be recorded in both the research database as well as dictated into the EMR, since these studies will be ordered as part of clinical care. The CRO will assist in analyzing trends of inter-reader correlation and variability.

Outcomes analysis: We will analyze the differential outcomes, between the two cohorts, as well as between the projected and actual outcomes within the contrast cohort, in these specific categories: diagnoses, number and types of subsequent imaging studies, pathology results, therapies, and related costs (defined as gross hospital charge), within the study period and extending 1 year afterward. The CRO will assist in analyzing variation within these metrics between the non-contrast vs. contrast cohorts. The CRO will also assist in analysis of variation between the projected outcomes and actual outcomes within the contrast cohort.

Risks vs Benefits

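### Aim 2's projected non-contrast course has no stated masking or lock and is never checked against the control cohort, so projection error of either sign cannot be separated from a contrast effect

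*Combined protocol and SAP*

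**What the plan says.** Study Design, Aim 2, has two interpretations recorded for every Gadoterate-enhanced exam, one from the non-contrast images alone and one from the whole exam. It continues: "We will subsequently record the *predicted* outcome data, as described above". The items are diagnoses, later imaging, pathology results, therapies and projected costs, and they are those "that would be associated with the more limited interpretation of the non-contrast images". The next step is: "Comparison to the actual outcomes of that patient will subsequently be analyzed".

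The method is justified by the statement that "the vast majority of the clinical MRI indications in this study have a well-defined diagnostic/therapeutic pathway", with two worked examples: a solitary liver lesion and cystic renal lesions. No complete pathway table is given.

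Two safeguards apply to the reads. Aim 2 initially blinds readers to history and prior exams. Under Analysis, Image analysis: "For the contrast exams, the interpreting radiologists will first render an evaluation based upon" the non-contrast images alone.

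Analysis, Outcomes analysis, lists two comparisons: one between the cohorts, and one "between the projected and actual outcomes within the contrast cohort". Neither applies the projection to control patients. The Statistics section plans 136 patients per cohort and gives no calculation for the projected-versus-actual comparison.

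**The concern.** In this analysis the comparator is a course that somebody writes down, not one that was observed. The blinding and reading order in the plan protect what goes into the projection (the non-contrast read). They do not cover the step from that read to a list of procedures, results and charges. The plan does not say who takes that step, what they may see, by what rules they work, or when the entry is closed. As written it follows both reads, so the contrast result already exists.

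Pathology is the sharpest case. A non-contrast read cannot supply the result of a biopsy that was never taken. The only patient-specific source is that patient's own later record.

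At stake is how the within-patient result bears on Hypothesis 2. Readers may lean on it because each patient serves as their own comparator, whereas the cohort comparison is open to selection: patients who decline Gadoterate are asked to form the non-contrast arm (Selection). The controls also have a recorded non-contrast read and an observed later course, so the study holds the material for a direct check and does not plan to use it.

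**Working it through.** The plan gives no figure for this comparison, so there is none to reproduce. The check has three parts.

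**1. What each safeguard covers**

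| Step | Protection stated |
|---|---|
| Non-contrast read | Rendered first; readers initially blinded to history and prior exams |
| Full read | Initially blinded to history and prior exams |
| Projection from the non-contrast read | None stated |
| Projected versus actual | No calibration stated |

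**2. Where projection error goes**

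For a Gadoterate patient let P be the projected value, A the actual value, and N the value that non-contrast care would really have produced. Then

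mean(P - A) = mean(N - A) + mean(P - N).

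The first term is the contrast effect and the second is projection error. The contrast cohort alone gives only their sum. In a control the observed course is N, so mean(projected - observed) in controls estimates the second term, subject to differences between the cohorts.

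As an illustration, take a yes/no procedure, 136 pairs (Statistics) and no true contrast effect. The other inputs are assumptions, not figures from the plan: a fraction q actually has the procedure, the projection adds one with probability u, and it misses one with probability v. The expected false difference is (1 - q)u - qv. The last column is the share of 4,000 simulated trials in which an exact paired (McNemar-type) test was significant at 5%.

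| q | u | v | False difference | Significant |
|---|---|---|---|---|
| 0.3 | 0.10 | 0 | 0.7×0.10 = +7.0 points | 92% |
| 0.3 | 0.05 | 0 | 0.7×0.05 = +3.5 points | 35% |
| 0.3 | 0.10 | 0.10 | 0.07 - 0.03 = +4.0 points | 23% |
| 0.5 | 0.10 | 0 | 0.5×0.10 = +5.0 points | 68% |
| 0.5 | 0.10 | 0.10 | 0.05 - 0.05 = 0 points | 2.5% |
| 0.7 | 0.10 | 0.10 | 0.03 - 0.07 = -4.0 points | not simulated |

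A positive value favours contrast. The sign depends on the error pattern, which the plan does not let anyone estimate.

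**3. What a check in the controls could show**

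For a paired difference with b = (1 - q)u and c = qv, the standard error is √([b + c - (b - c)²]/n).

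- q = 0.5, u = v = 0.10, n = 136: b = c = 0.05, so the 95% half-width is 1.96×√(0.10/136) = 0.053.
- q = 0.3, u = 0.10, v = 0, n = 136: b = 0.07, c = 0, so it is 1.96×√((0.07 - 0.0049)/136) = 0.043.
- Contrast-cohort difference minus control calibration error, with the first inputs in both cohorts: 1.96×√(2×0.10/136) = 0.075.
- One indication, assuming six equal groups (five mass sites and vasculature), so 136/6 ≈ 23 controls: 1.96×√(0.10/23) = 0.129.

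Under these assumptions the controls fix the overall calibration error to about 4 to 5 points, and within one indication only to about 13. These figures are for a yes/no outcome and do not carry over to imaging counts or charges.

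**The case against.** Four stronger readings are tempting, and the documents support none of them.

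- *The projection is written with the actual course in view, by unmasked staff.* The order in Aim 2 is reads, projection, comparison. The projection follows the reads, but nothing places it after the outcomes. On masking the text is silent, and silence does not show that projectors are unmasked.
- *The plan rules blinding out.* The sentence saying that blinding is unnecessary is in the Gadoterate section, beside storage and administration. It concerns the contrast agent and says nothing about projections.
- *The error must favour contrast.* In both worked examples the non-contrast path adds a procedure, so over-projection is plausible. But error can be neutral or run the other way, as the table shows, and borrowing diagnosis or pathology from the actual course would pull the projection towards that course and shrink the difference.
- *Hypothesis 2 rests on projections.* Aim 2 introduces this analysis as further exploration, and the between-cohort comparison uses observed outcomes only.

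Two practical objections stand in part. Calibration is not free, because projections are now planned only for the contrast cohort. It may also transfer imperfectly: controls include patients who declined Gadoterate and some who consented after their MRI. Both points limit the check without removing the need for it, because without it the size of the error stays unknown.

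**Conclusion.** The point holds as a gap in a supporting analysis. The projection has no stated masking, lock or complete rule set, and it is not compared with observed non-contrast care. Whatever error it carries passes one for one into the projected-versus-actual result and cannot be separated from a contrast effect. The documents give no basis for its size or direction. The range of +7 to -4 points rests wholly on the assumed q, u and v, and shows only that modest error rates could matter with 136 pairs. The comparison of observed outcomes between cohorts is unaffected. The change is worth making before projections are entered; it is a better method at small cost, and the rest of Aim 2 stands without it.

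**What to change.** Amend Study Design, Aim 2, and Analysis, Outcomes analysis, as follows.

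1. Enter and lock the projection together with the non-contrast read, before the contrast series is opened, using one pre-written, indication-specific pathway table. Project whether a biopsy occurs, not its result.
2. Apply the same table to each control's non-contrast research read, made under the same blinding to history. Compare projected with observed imaging, biopsy, therapy and charges. Adjust for indication and baseline characteristics, because controls are partly self-selected. Care follows final reads made with history in both cohorts, so using the blinded read in both keeps that feature alike.
3. Report the projected-versus-actual result beside the control projected-minus-observed difference and its confidence interval, overall and not by indication. Describe it as a contrast effect only to the extent that it exceeds that calibration error.

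The cost is a written table, a time-stamped lock and up to 136 additional table-based projections; no patient's care changes. The downsides are imperfect transfer of the calibration from self-selected controls, a wider interval once calibration error is taken into account, and possibly a smaller reported benefit.

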Each patient's GFR will be recorded prior to the exams and 48-72 hours after scanning. In addition, each patient will be contacted at baseline as well as 6 weeks, 3 months, and 6 months post-scan to comprehensively evaluate for any symptoms or signs of NSF (see attached sheet) [19]. If at any point a patient's follow-up interviews indicate they might be experiencing symptoms of NSF, or if their post-MRI research blood draw indicates deteriorating renal function, the study PI will be notified and the patient will be referred for further medical evaluation, if necessary. All relevant demographics, such as hypertension, diabetes, coronary artery disease, and liver disease, will be recorded. The data will be analyzed, using standard statistical methods, for any significant and disparate variations in renal function.

Aim 2:

Each MRI exam will be independently interpreted by 2 participating sub-specialty-trained (either neuro or body) radiologists. To limit bias, the readers will initially be blinded to history and prior exams and their respective interpretations recorded in the research database (history and prior exams will subsequently be provided, as usual, for the final interpretations used in clinical care). The interpretations and inter-reader correlation will be recorded for each exam. Via Loyola electronic medical record (EMR) we will record the chronology of all subsequent related diagnoses, imaging studies, pathology results, therapies, and related costs (defined as gross hospital charge), within the study period (1-2 years) and for one year afterward. These data will be analyzed to compare differential outcomes between the non-contrast and contrast cohorts.

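### Aim 2's supplementary projected-versus-actual comparison varies more than contrast (apparently access to history, and modelled against observed outcomes), so its difference cannot be credited to contrast alone

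*Combined protocol and SAP*

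**What the plan says.** Under Study Design, Aim 2, the plan states for every exam that "the readers will initially be blinded to history and prior exams and their respective interpretations recorded in the research database", and that "history and prior exams will subsequently be provided, as usual, for the final interpretations used in clinical care". For the contrast cohort it adds that "two separate interpretations for each Gadoterate-enhanced MRI will be recorded in the research database": one from the non-contrast images only and one from the whole exam. It then has staff record the predicted diagnoses, imaging, pathology, therapies and costs "that would be associated with the more limited interpretation of the non-contrast images". The next step is: "Comparison to the actual outcomes of that patient will subsequently be analyzed". The stated justification is that most of the study's MRI indications "have a well-defined diagnostic/therapeutic pathway".

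The Image analysis section repeats that exams are interpreted "with the readers blinded to history and prior exams". It says that contrast exams are read first on the non-contrast images alone, and that "these interpretations will be recorded only within the research database". The overall contrast interpretation goes into both the research database and the medical record. The Outcomes analysis section lists two comparisons: between the cohorts, and projected against actual within the contrast cohort.

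**The concern.** The Image analysis section says that reading the non-contrast images first will allow the added value of contrast to be evaluated. That requires the two sides of the within-patient comparison to differ only in contrast. As written, they appear to differ in the reader's access to history and prior exams as well, and they certainly differ in how the outcome is obtained.

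The plan's own examples show how this could matter. An indeterminate liver lesion goes to biopsy, and an uncharacterised renal cyst goes to serial imaging. If a prior exam would have settled some of these cases without contrast, a blinded non-contrast read would project a biopsy or a repeat scan that informed care would have avoided, and contrast would be credited with avoiding it. Equally, actual care can leave the pathway (refusal, death, unplanned repeat scans), which can widen or narrow the gap. A difference could be credited to contrast that contrast did not cause, or a real effect could be hidden.

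**Working it through.** The plan states no figure for this comparison, so there is none to reproduce. The check is to trace what feeds each side.

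| Feature | Projected side | Actual side | Source |
|---|---|---|---|
| Contrast images | No | Yes | Aim 2 |
| History and prior exams at the read | Apparently no | Yes | Aim 2 with Image analysis (inference) |
| Read drives care | No, research database only | Yes, in the medical record | Image analysis |
| Outcome | Modelled along a standard pathway | Observed in the medical record | Aim 2 |

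The second row combines two places: initial reads are blinded (Aim 2), and the non-contrast read of a contrast exam comes first and stays in the research database (Image analysis). No single sentence says it, and none contradicts it. The last row needs only the Aim 2 text.

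The plan does not provide for a non-contrast read made with history, or for outcomes projected from the full read. It does not say who makes the projections, or whether that person sees the chart or the actual outcomes.

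**Between-cohort comparison.** Final clinical reads in both cohorts use history, and both sets of outcomes are observed. The problem above does not arise there.

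**How the components mix (assumed values).** Let h be the share of non-definitive results that history alone would resolve and c the share that contrast alone would resolve. If the two add, and projection error is ignored:

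projected minus actual = h + c

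- With c = 0 and h = 5%, 10% or 20%, the gap is 5, 10 or 20 points (136 × h = 6.8, 13.6 or 27.2 patients), although contrast did nothing.
- With c = 10%, the same h gives 15, 20 or 30 points.

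**Effect on a paired test (assumed values; the plan names no test).** Take one yes/no step in 136 patients and an exact two-sided McNemar test, rejecting at p ≤ 0.05. For b changes one way and k the other, p = 2 × P(X ≤ min(b, k)), with X ~ Binomial(b + k, ½). Power sums this rule over the discordant count, Binomial(136, p₁ + p₂), and its split, Binomial(m, p₁/(p₁ + p₂)).

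| Assumed contrast effect | Nothing added | 3% added the other way | 5% added the other way |
|---|---|---|---|
| 10% v 2% | net 8 points, power 74% | net 5 points, power 25% | net 3 points, power 9% |
| 30% v 5% | net 25 points, power about 100% | net 22 points, power 99% | net 20 points, power 96% |

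If 3% is added in the same direction, 10% v 2% becomes 13% v 2% and power rises to 92%. With a small effect the conclusion can be lost; with a large one the test still rejects. In both rows the net difference is wrong by the amount added. These figures show sensitivity and do not estimate the bias.

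**The case against.** - **The history gap is an inference.** This stands. Aim 2 does not say what the person making the projection can see, and an open chart would narrow the information gap. A reader might infer that the projection is definitely blind to history; the documents do not establish that. The modelled-versus-observed difference remains either way.
- **The comparison is supplementary.** This stands. The plan introduces it as further exploration, Specific Aim 2 is to establish a database, and this is a single-site pilot. No test, threshold or decision is attached to it.
- **Any within-patient counterfactual must be modelled on the unobserved side.** True. Modelling both sides gives up observed outcomes and leans on the pathway table. That is a reason to keep both analyses, each labelled for what it estimates. It does not make the planned difference a contrast effect.
- **The expected effects are large.** The Statistics section anticipates differentials far above 5%. At 30% v 5% a modest distortion would rarely overturn a significant result. This limits the consequence for testing, but the estimated size of the benefit, including charges, would still be distorted.
- **A matched pair of blinded reads may not be stored.** Aim 2 suggests that a blinded full read is recorded. The stored full interpretation could instead be the with-history clinical read, since the overall contrast interpretation also goes into the medical record. The fix allows for this.

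**Conclusion.** The point holds, as a minor one. The projected-versus-actual difference combines the effect of contrast, apparently the effect of history and prior exams, and the gap between modelled and observed care. It cannot be attributed to contrast alone.

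The information part rests on reading Aim 2 and Image analysis together; the modelled-versus-observed part rests on Aim 2 alone. All percentages above are assumptions.

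Two stronger readings are tempting and are not supported. One is that the bias favours contrast: missing history could inflate the apparent benefit, but departures from the pathway can act either way, and the documents give no rates. The other is that Aim 2's outcome analysis fails as a whole: the between-cohort comparison does not have this defect. It has a separate weakness, because patients who decline Gadoterate are asked to form the non-contrast arm (Selection section).

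**What to change.** Amend Aim 2 and Outcomes analysis as follows.

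1. For each Gadoterate exam, record the non-contrast-only and the full interpretation as separate entries, made with the same information and both before history and prior exams are supplied. If the blinded full read is not already stored, this is one more entry by the same readers. State in advance how the two readers' interpretations are combined, so that each exam yields one pair.
2. Project both entries through one prespecified pathway table over the same horizon, before actual outcomes are looked up. Analyse them as paired data (for example McNemar for yes/no steps, Wilcoxon for counts and charges). Name this as the analysis that isolates contrast, for readers without history.
3. Keep projected versus actual as a descriptive analysis, and state that its difference is not attributed to contrast alone.
4. Optionally, apply the same table to the blinded reads of the non-contrast cohort. Contrast is absent there, so projected versus actual shows the combined effect of history and projection error. It cannot separate the two, and it is only a guide because the cohorts are self-selected.

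**Cost.** Revised wording, a pathway table and more abstraction; no new patients, scans or readers. The documents state no planned number of projections. With one combined pair per exam, the contrast cohort needs 2 × 136 = 272, twice what one projection per exam would need; the optional step adds 136, giving 408.

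**Downsides.** The paired result rests on projected outcomes, applies to readers without history, and keeps the fixed order of non-contrast images first.

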$$\text{eGFR} = \frac{(140 - \text{Age}) \times \text{Mass (kg)} \times (0.89 \text{ if female})}{72 \times \text{serum creatinine (mg/dL)}}$$

Exclusion Criteria: Pregnant and lactating females; planned initiation of chemotherapy or surgery within 72 hours of the MRI exam; hemodynamic instability or acute coronary syndrome; history of the following nephrotoxic medications within 2 weeks of the exam: Amphotericin B, Lithium, Pentamidine, Aminoglycosides, Acyclovir, Gancyclovir, or Foscavir; age less than 18 years.

Note that many patients within the inclusion criteria may have pre-existing conditions which could, theoretically, cause a GFR decrease unrelated to the Gadoterate in the 48-72 hour post-injection window; however, such cases will be statistically represented in both cohorts and, as such, are not expected to affect the comparisons between the two populations due to the sufficient statistical power of the study.

Recruitment

Patient recruitment will occur via two complementary mechanisms: In the clinician office when the study is ordered and via the research nurse and/or study coordinator. It is expected that a significant component of patients will be recruited into the study by the clinicians in the participating departments. Education of clinicians in these departments is ongoing at this time and all have been enthusiastic about participating. In addition, the nurse coordinator will review the radiology informatics system, on a daily basis, to identify all eligible patients for whom non-contrast MRIs have been ordered due to GFR concerns. In such cases the nurse coordinator will contact the study PI to determine eligibility. If the patient meets eligibility criteria, the study PI will confirm with the patient's ordering physician. The patient will be contacted and the study PI, sub-investigator, or other appropriate study staff will explain the study, with its risks and benefits, to the patient at least 8 hours prior to the MRI exam. The study PI or sub-investigator will contact the ordering physician prior to the date of the exam to obtain an updated order allowing for contrast MRI. Signature of the consent form itself will then be available for the patient at the time of the exam. In either of these scenarios a patient who does not want Gadoterate contrast will receive the usual non-contrast MRI.

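### Entry requires a GFR below 30 but not stable or chronic disease, while the Aim 1 benchmark comes from chronic kidney failure patients; Aim 1 results should be reported by pre-scan renal stability.

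*Combined protocol and SAP*

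**What the plan says.** Eligibility (Study Design; Study Procedures, Subject selection): "Inclusion Criteria: GFR less than 30 ml/min, but not on dialysis, with indications for MRI as described above". The exclusions bearing on acute change are hemodynamic instability, acute coronary syndrome, a list of nephrotoxic drugs within 2 weeks, and chemotherapy or surgery due to start within 72 hours of the exam. Nothing asks for a second GFR, a minimum duration, a stable creatinine or a chronic kidney disease diagnosis, and acute kidney injury is not excluded.

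Benchmark (Statistics): "Previously-tested GBCAs in chronic kidney failure patients have resulted in 10-25% rates of decreased GFR", "with most investigations recording rates in the range of ~15" per cent. Against that, "the rate is expected to be no more than 5% using Gadoterate". The size is set "with a power of 90% and a 5% significance", and "a sample size of approximately 136 patients receiving Gadoterate is properly powered to address Aim 1". The control arm need not be that large for Aim 1, but "it will consist of 136 patients as well, to properly power analysis of Aim 2".

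Outcome (Study Design, Aim 1): GFR before the exam and again 48-72 hours after it.

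Unrelated change: the note after the Exclusion Criteria accepts that many eligible patients may have conditions that "could, theoretically, cause a GFR decrease unrelated to the Gadoterate in the 48-72 hour post-injection window". It expects no effect on the comparison, because such cases will occur in both cohorts and the study has enough power. It does not mention improvement.

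Cohorts (Selection; Recruitment): patients who decline Gadoterate are invited to be controls, and some controls are enrolled after a completed non-contrast MRI.

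**The concern.** The benchmark is described as a chronic population, and entry does not require one. Two or three days is long enough for acute injury to move GFR by itself. A patient recovering from acute injury enters with a low value that then rises, so a small harmful effect would not register as a decrease. A patient whose injury is still developing may be counted as an event that Gadoterate did not cause.

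The first direction matters more in a safety study, because it makes the agent look safer than it is, and it is the one the plan does not discuss. The Background section says that these pilot data are meant to lead to a larger multi-site trial. A favourable rate that partly reflects recovery would be carried forward as evidence of renal safety.

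**Working it through.** **The plan's own figure.** Inputs from Statistics: 15% v 5%, 90% power, 5% significance, sidedness not stated.

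- Two-sample, pooled: n per arm = [z_a√(2·0.10·0.90) + z_b√(0.15·0.85 + 0.05·0.95)]² / 0.10². This gives 188 two-sided and 153 one-sided.
- One-sample against a fixed 15%: n = [z_a√(0.15·0.85) + z_b√(0.05·0.95)]² / 0.10². This gives 96 two-sided and 76 one-sided.

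Neither gives 136. That is a separate matter and neither supports nor weakens this point. It does mean that the intended test cannot be read off the sample size. The illustrations below take 136 as given.

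**Reference test.** Exact binomial, n = 136, null rate 15%, one-sided 5%. The largest count with P(X ≤ c | 136, 0.15) ≤ 0.05 is c = 13, with an actual error of 4.3%. Power at a true 5% is P(X ≤ 13 | 136, 0.05) = 99.2%.

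**Assumptions.** The documents give neither the share f of patients with acute change nor their event rate. Both are varied here.

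*Recovering patients, no events; true rate 15% in the others.* Overall rate = 0.15(1 − f); false success = P(X ≤ 13).

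| f | overall rate | chance of falsely declaring a rate below 15% |
|---|---|---|
| 0 | 15% | 4.3% |
| 10% | 13.5% | 10.8% |
| 20% | 12% | 23% |
| 30% | 10.5% | 43% |

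*Worsening patients with a 30% event rate; true rate 5% in the others.* Overall rate = 0.05(1 − f) + 0.30f.

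| f | overall rate | power |
|---|---|---|
| 0 | 5% | 99% |
| 10% | 7.5% | 86% |
| 20% | 10% | 50% |
| 30% | 12.5% | 18% |

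*Both together.* The two can cancel. With 10% recovering (no events), 10% worsening (30% events) and 15% in the rest, the overall rate is 0.80·0.15 + 0.10·0 + 0.10·0.30 = 15%.

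**Does the control cohort deal with it?** In a two-arm comparison of 136 v 136 with no drug effect, equal acute shares leave the chance of falsely finding Gadoterate lower at its nominal 2.5%. If worsening patients (30% event rate, 5% in the rest) make up 10% of the Gadoterate cohort and 30% of controls, the rates are 7.5% v 12.5% and that chance is 28%. Controls therefore help only if the shares are similar. With allocation by patient choice the design does not secure that, and a larger sample would make the false difference easier to detect, not smaller. In a comparison with the historical 15%, controls play no part.

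**The case against.** Several counter-arguments have force.

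- *Planned, ambulatory patients.* Office recruitment, a discussion at least 8 hours ahead and a paid return visit for the blood draw all suggest this, and the document never mentions inpatients. On the other side, Consent provides for proxies when stroke, injury or hepatic encephalopathy prevents consent, and Risks vs Benefits says that ill patients are often the ones denied contrast. Some acute change is to be expected; a large share is not shown.
- *The exclusions.* They cover more than circulatory instability and drugs: chemotherapy or surgery about to start is also excluded, and the investigator checks eligibility of patients found by the coordinator. This narrows the gap, but none of it requires stable renal function.
- *The benchmark studies.* Whether they required stability cannot be checked here. The label chronic is the protocol's own.
- *No written test against 15%.* The figure appears in the sample-size rationale, and other passages speak of comparing the cohorts. This stands, and it is why the fix covers both comparisons.

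A reader might infer three stronger things that the documents do not support.

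1. That Aim 1 should be analysed mainly in stable chronic disease and its conclusions limited to that. Hypothesis 1 concerns patients with GFR below 30 in general, so this would change the question. It would also cost power: if 40% were set aside, 0.6 × 136 ≈ 82 remain, and exact power against 15% is 88% at one-sided 5% or 77% at one-sided 2.5%.
2. That regression to the mean seriously distorts the result. That the qualifying value is also the baseline is an inference. In a simulation with an assumed median GFR of 22-25 before selection and a within-patient CV of 5-15%, the second value averages only about 0.2-3.5% higher. Benchmark patients may carry the same artefact.
3. That a low observed rate would be an artefact. No acute share is given, and the two directions can offset each other.

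**Conclusion.** The point holds as a gap in design and reporting, not as proof of a biased result. On the text, stability and chronicity are not required, the benchmark is labelled chronic, and the outcome window is short. The assurance that power takes care of unrelated change is wrong in principle.

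The size cannot be derived from the documents. If 10-20% of patients were recovering and event-free, false success against 15% would go from 4.3% to 11-23%. If the same share were worsening with a 30% event rate, power would fall from 99% to between 86% and 50%. These figures rest on the assumed shares and event rates and on an exact one-sided 5% test that the plan does not itself specify. The plan also states no size of decrease, so an event here means whatever definition underlies the 15%. This is a cheap improvement worth making; it does not invalidate Aim 1.

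**What to change.** Keep every patient with GFR below 30 as the main Aim 1 population, and add the following to the Statistics and Aim 1 text.

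1. Before any 48-72 hour result is reviewed, classify each patient in both cohorts as stable, unstable or unknown. Use creatinine values already in the medical record and dated before the scan, under a definition that the investigators fix in advance.
2. Report the 48-72 hour decreased-GFR rate by stratum and by cohort.
3. Adjust the between-cohort comparison for stratum. At a 5% rate only about 7 events are expected among 136 patients (0.05 × 136 = 6.8), so a simple stratified estimate such as Mantel-Haenszel is suitable.
4. Present the comparison with the roughly 15% rate in the stable stratum as a pre-specified sensitivity analysis, and let it qualify any claim made against that benchmark.
5. Replace the sentence that relies on statistical power in the note after the Exclusion Criteria. Say instead that acute change may go in either direction, that balance between self-selected cohorts is not assured, and that stratified results will be shown.

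The baseline definition need not change. The cost is chart abstraction and analysis text, with no added blood draw. Some patients will be unknown, and estimates within strata will be less precise than the overall one.
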